3.2 Scientific rationale for study design

See Section 1.2.

3.3 Justification for dose

The dose of olaparib used in this study is 300 mg twice daily which is the currently FDA approved dose. Starting dose modifications based on the patient's medical condition, for example creatinine clearance, are allowed.

3.4 End of study definition

The end of study is defined as 7 months from enrolment. This is to include the one-month follow up physical exam, concomitant medications, adverse effects, and folate level

Clinical Study Protocol - 6
Olaparib - ESR-18-13807

4. STUDY POPULATION

This study will include all patients with solid tumors who can benefit from olaparib therapy for the treatment of their malignancy as determined by their primary oncologist.

Prospective approval of protocol deviations to recruitment and enrolment criteria, also known as protocol waivers or exemptions, may be permitted by the principal investigators.

Each patient should meet all of the inclusion criteria and none of the exclusion criteria for this study in order to assigned/randomised to a study intervention Patients, who do not meet the entry requirements are deemed as screen failures, refer to Section 5.4.

4.1 Inclusion criteria

Patients are eligible to be included in the study only if all of the following inclusion criteria and none of the exclusion criteria apply:

Informed consent

1. Capable of providing a signed informed consent which includes compliance with the requirements and restrictions listed in the informed consent form (ICF) and in this protocol.
2. Provision of signed and dated, written informed consent form prior to any mandatory study specific procedures, sampling, and analyses.
3. For inclusion in the optional biomarker research, patients must fulfil the following criteria:
 - Provision of informed consent for biomarker research prior to collection of sample

If a patient declines to participate in the optional biomarker research, there will be no penalty or loss of benefit to the patient. The patient will not be excluded from other aspects of the study.

Age

4. Patient must be ≥ 18 years of age inclusive, at the time of signing the informed consent form.

Type of patient and disease characteristics

Patients with solid tumors harboring molecular alterations which are likely to respond olaparib, such as germline and somatic mutations in *BRCA1* and *BRCA2* genes, other genes in Homologous DNA Recombination Repair (HRR) pathway, genomic stability as determined by Homologous Recombination Deficiency (HRD) assay, etc. Olaparib must be recommended to these patients by their treating physician.

Clinical Study Protocol - 6
Olaparib - ESR-18-13807

6. Patients must have normal organ and bone marrow function measured within 28 days prior to administration of study treatment as defined below:
- Haemoglobin ≥ 10 g/dL with no blood transfusion in the past 28 days
 - Absolute neutrophil count (ANC) $\geq 1.5 \times 10^9/L$
 - Platelet count $\geq 100 \times 10^9/L$
 - Total bilirubin ≤ 1.5 x institutional upper limit of normal (ULN)
 - Aspartate aminotransferase (AST) (Serum Glutamic Oxaloacetic Transaminase (SGOT)) / Alanine aminotransferase (ALT) (Serum Glutamic Pyruvate Transaminase (SGPT)) ≤ 2.5 x institutional upper limit of normal unless liver metastases are present in which case they must be ≤ 5 x ULN
 - Patients must have creatinine clearance estimated of ≥ 51 mL/min using the Cockcroft-Gault equation or based on a 24 hour urine test :

$$\text{Estimated creatinine clearance} = \frac{(140 - \text{age [years]}) \times \text{weight (kg)}}{\text{serum creatinine (mg/dL)}} \times F^a$$

^a where F=0.85 for females.

7. Eastern Cooperative Oncology Group (ECOG) performance status 0-1).
8. Patients must have a life expectancy ≥ 16 weeks.
9. Patients with measurable and non-measurable disease are eligible.
10. There is no limit on the number of prior therapy lines. Olaparib can be used in the front or a subsequent lines of therapy as well as maintenance.
11. Patients can be enrolled with the lab results outside of the Inclusion criteria range or a performance status = 2, if olaparib is recommended by their treating oncologist/physician and the olaparib Package Insert is followed for dose adjustments.

Sex

12. Female or male

Clinical Study Protocol - 6
Olaparib - ESR-18-13807

Reproduction

13. Postmenopausal or evidence of non-childbearing status for women of childbearing potential: negative urine or serum pregnancy test within 28 days of study treatment and confirmed prior to treatment on day 1.

Postmenopausal is defined as:

- Amenorrheic for 1 year or more following cessation of exogenous hormonal treatments
 - Luteinizing hormone (LH) and Follicle stimulating hormone (FSH) levels in the post-menopausal range for women under 50
 - radiation-induced oophorectomy with last menses >1 year ago
 - chemotherapy-induced menopause with >1 year interval since last menses
 - surgical sterilisation (bilateral oophorectomy or hysterectomy)
14. Advise male patients with female partners of reproductive potential or who are pregnant to use effective contraception during treatment and for 3 months following the last dose of olaparib and to not donate sperm during this time.

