5.6 Dose modification

Dose Reductions

Clinical Study Protocol - 6
 Olaparib - ESR-18-13807

In case a dose reduction is necessary, the Study treatment will be administered as follows:

Table 4 Dose reductions for olaparib to manage adverse events

Initial Dose	Following re-challenge post interruption: Dose reduction 1	Dose reduction 2
300 mg twice daily	250 mg twice daily	200 mg twice daily
250 mg twice daily	200 mg twice daily	150 mg twice daily
200 mg twice daily	150 mg twice daily	100 mg twice daily

Table 5 Dose reduction for olaparib if patient develops moderate renal impairment

Initial Dose	Moderate renal impairment (calculated creatinine clearance by Cockcroft -Gault equation or based on a 24 hour urine test between 31 and 50 ml/min): Dose reduction
300 mg twice daily	200 mg twice daily

If starting dose is 200 mg twice daily, and patient develops renal impairment, dose modification will be determined by the treating physician.

Table 6 Dose reductions for olaparib if patient has to start taking a strong or moderate CYP3A inhibitor

Initial Dose	Strong CYP3A inhibitor	Moderate CYP3A inhibitor
300 mg twice daily	100 mg twice daily	150 mg twice daily

If starting dose is 200 mg twice daily, and patient is required to take a strong or moderate CYP3A inhibitor, dose modification will be determined by the treating physician.

For guidance on dose reductions for management of AEs (including renal impairment) refer to Section 8.4.4.

For guidance on dose reductions when concomitant strong or moderate CYP3A inhibitors cannot be avoided see Section 6.5.

When dose reduction is necessary patients will take one 150 mg tablet and one 100 mg tablet twice daily or two x 100 mg tablet twice daily (see Section 8.4.4), or one 150 mg tablet twice daily or one 100 mg tablet twice daily (see Section 6.5).

Folic Acid dose modification:

Clinical Study Protocol - 6
Olaparib - ESR-18-13807

Patients with folate deficiency will start folic acid supplementation at 1 mg daily. If they continue to have a Hgb less than 10 g/dl (grade 2) and folate deficiency despite folate supplementation, folic acid dose can be increased to 2 mg daily or higher at the discretion of the investigator.

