7.4.4.9 Renal impairment

If subsequent to study entry and while still on study therapy, a patient's estimated CrCl falls below the threshold for study inclusion (≥ 51 ml/min), retesting should be performed promptly.

A dose reduction is recommended for patients who develop moderate renal impairment (calculated creatinine clearance by Cockcroft-Gault equation or based on a 24 hour urine test of between 31 and 50 ml/min) for any reason during the course of the study: the dose of olaparib *or* should be reduced to 200 mg twice daily.

Because the CrCl determination is only an estimate of renal function, in instances where the CrCl falls to between 31 and 50 mL/min, the investigator should use his or her discretion in determining whether a dose change or discontinuation of therapy is warranted.

Clinical Study Protocol - 6
Olaparib - ESR-18-13807

Olaparib has not been studied in patients with severe renal impairment (creatinine clearance ≤ 30 ml/min) or end-stage renal disease; if patients develop severe impairment or end stage disease is it recommended that olaparib be discontinued.

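### As it reads in the available text, the creatinine-clearance formula in inclusion 6 is not the Cockcroft-Gault equation it names and gives values 72 times too large for the protocol's own mL/min limits

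*Combined protocol and SAP*

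**What the plan says.** Section 4.1, item 6, sets the renal entry requirement: "Patients must have creatinine clearance estimated of ≥ 51 mL/min using the Cockcroft-Gault equation or based on a 24 hour urine test". The formula beneath it has 140 minus age in years, times weight in kg, as the numerator. The only term in the denominator is "serum creatinine (mg/dL", and the quotient is multiplied by a factor F. The footnote says "where F=0.85 for females" and gives no value for males, although item 12 admits both sexes.

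Two other places rely on the same named equation without reprinting it:

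- Section 5.6, Table 5: "Moderate renal impairment (calculated creatinine clearance by Cockcroft -Gault equation or based on a 24 hour urine test between 31 and 50 ml/min".
- Section 7.4.4.9: "calculated creatinine clearance by Cockcroft-Gault equation or based on a 24 hour urine test of between 31 and 50 ml/min". This section also calls for retesting when clearance drops below the entry limit of 51, and defines a severe category: "Olaparib has not been studied in patients with severe renal impairment (creatinine clearance ≤ 30 ml/min) or end-stage renal disease".

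Several provisions make the entry limit flexible. Item 11 of section 4.1 admits patients whose laboratory values are out of range if the treating physician recommends olaparib and dose adjustments follow the package insert. Section 4 lets the principal investigators approve waivers of enrolment criteria. Section 4.2, item 11, allows exceptions case by case. Section 3.3 allows the starting dose to be modified for creatinine clearance.

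**The concern.** The protocol works on a clearance scale with cut-offs at 51, 31 to 50, and 30 mL/min. The printed formula does not produce numbers on that scale. For ordinary patients it returns thousands, so a comparison with 51 carries no information.

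The practical stake is recognition. Item 11 does not wave through every out-of-range patient: it attaches a condition about dose adjustment. That condition operates only if the site knows that the value is out of range. A site that computes clearance from the printed line would record a pass and have no reason to consider item 11. The study is multi-centre (section 3.1), so sites may also compute clearance in different ways.

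**Working it through.** **Inputs from the documents.** Formula as printed: (140 − age) × weight / creatinine × F, with F = 0.85 for females. Limits: at least 51 (entry), 31 to 50 (moderate), 30 or less (severe), all in mL/min.

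**Inputs assumed.** The constant 72 is the standard Cockcroft-Gault divisor for creatinine in mg/dL. F = 1 for males. The patient values below are illustrative.

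**Step 1: mismatch without any outside constant.** For a woman aged 60, 70 kg, the printed formula gives 80 × 70 × 0.85 / creatinine = 4,760 / creatinine. To fall below 51 she would need a creatinine above 4,760 / 51 = 93.3 mg/dL. To land in the 31 to 50 band she would need between 4,760 / 50 = 95.2 and 4,760 / 31 = 153.5 mg/dL. The printed line and the printed limits therefore do not belong to the same scale, whatever the correct divisor is.

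**Step 2: size of the error with 72.** Each result is divided by 72.

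| Patient | As printed | With 72 | Protocol band with 72 |
|---|---|---|---|
| F, 60 y, 70 kg, 1.0 mg/dL | 80 × 70 / 1.0 × 0.85 = 4,760 | 66.1 | at least 51 |
| M, 60 y, 70 kg, 1.0 mg/dL | 80 × 70 / 1.0 × 1 = 5,600 | 77.8 | at least 51 |
| F, 65 y, 60 kg, 1.2 mg/dL | 75 × 60 / 1.2 × 0.85 = 3,187.5 | 44.3 | 31 to 50 |
| F, 80 y, 50 kg, 2.5 mg/dL | 60 × 50 / 2.5 × 0.85 = 1,020 | 14.2 | 30 or less |
| F, 85 y, 45 kg, 5 mg/dL | 55 × 45 / 5 × 0.85 = 421 | 5.8 | 30 or less |
| F, 90 y, 40 kg, 10 mg/dL | 50 × 40 / 10 × 0.85 = 170 | 2.4 | 30 or less |

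With 72 in place the results spread across the protocol's three bands, which supports it as the missing term. As printed, all six patients pass.

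**Step 3: can anyone fail the printed line?** A patient exactly at the intended limit scores 51 × 72 = 3,672. A printed score below 51 corresponds to a clearance below 51 / 72 = 0.71 mL/min. Take assumed ranges of age 18 to 95, weight 35 to 130 kg, creatinine 0.4 to 10 mg/dL, and either sex. The lowest printed value is at the extreme corner: (140 − 95) × 35 / 10 × 0.85 = 134. The highest is (140 − 18) × 130 / 0.4 × 1 = 39,650. None of 302,640 grid combinations falls below 51. These are grid points, not a patient distribution, so they say nothing about how many enrolled patients are affected.

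**Step 4: is it corrected elsewhere?** No. The formula is printed once; sections 5.6 and 7.4.4.9 give only the equation's name.

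**The case against.** **The constant may have been lost in conversion.** The available text is a machine conversion of a PDF, and formulas convert poorly. The inclusion list also jumps from item 4 through an unnumbered paragraph to item 6, so at least one numeral is missing either from the source or from the conversion. A dropped 72 would look the same. This objection stands. The numerator, unit, factor and footnote read intact, but only the source PDF can settle the matter.

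**Sites need not use the line.** The requirement is met by the named equation or by a 24-hour urine test. A standard calculator gives the right answer, and 4,760 mL/min would look absurd to most readers. This also stands and limits the practical effect. It does not make the printed formula correct.

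**The limit is soft anyway.** Item 11 of section 4.1, the waivers in section 4 and item 11 of section 4.2 all let out-of-range patients in. This stands against any claim that patients were wrongly admitted. It does not remove the concern that item 11's dose-adjustment condition goes unnoticed when the value is not recognised as out of range.

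**Stronger readings.** A reader might infer that the renal criterion can exclude no one, or that the dose bands in Table 5 and section 7.4.4.9 have also failed. The first holds only if the printed line is used literally and no urine test is done. The second is not supported, because those sections name the equation correctly, do not reprint the faulty line and do not refer back to it. A reader might also expect a knock-on effect on the haematological endpoints through renal function, but the documents state no such link.

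**Conclusion.** Wrong as written, of moderate severity, with confidence subject to the PDF check. The scale mismatch between the formula and the protocol's own limits follows from the documents alone. The factor of 72 rests on the standard form of the equation they name. Under literal use, over the assumed patient ranges, no value falls below 51 mL/min. The printed result is not always in the thousands: once the clearance with 72 is below about 1,000 / 72 = 13.9 mL/min it falls to hundreds, which still passes.

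How many patients are affected is unknown, and nothing in the documents shows that any site used the printed line. The primary endpoint, the sample size and the analysis plan do not depend on this formula.

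**What to change.** 1. Check inclusion 6 against the source PDF. If the constant is there, the point falls away apart from the missing F for males.
2. If it is absent, print the formula as (140 − age) × weight (kg) × F / (72 × serum creatinine [mg/dL]), with F = 0.85 for females and 1 for males.
3. Ask sites whether any clearance, at entry or on study, was computed from the printed line, and recompute those values. Any that prove out of range should be documented under the protocol's existing provisions, including item 11.

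No change to any clearance limit or dose rule is proposed. The cost is one line in an amendment, plus a recalculation from the age, weight and creatinine that the original computation already used.

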1. PROTOCOL SUMMARY

1.1 Schedule of Activities (SoA)

1. Participants will be screened for eligibility with medical history, physical exam, prior treatment, history of anemia and blood tests including baseline CBC, reticulocyte count, ferritin, B-12 and serum folate level
2. If inclusion criteria are met and after signing a consent form, participants will start olaparib 300 mg twice daily, commercially approved
3. Assessment of CBC/serum folate will occur every 2 weeks for the first 3 months and then monthly for a total of 6 months from the time of enrollment onto study therapy. If the patient develops folate deficiency and requires folate replacement, CBC/serum folate and reticulocyte count will occur every 2 weeks for 12 months.
4. One-time measurement of serum folate to occur one month after completion or discontinuation of therapy with olaparib
5. If folate deficiency is identified (defined as any level below normal) at any time point, the following parameters will be assessed in 2 weeks or at the next visit/assessment point: a repeat CBC/serum folate level along with B-12, LDH, reticulocyte count, methylmalonic acid, and homocysteine. These labs (CBC/serum folate level, B-12, LDH, reticulocyte count, methylmalonic acid, and homocysteine) need to be drawn once- 2 weeks after initial folate deficiency is identified for confirmation purposes and to rule out co-existing B-12 deficiency or other causes of anemia.
6. Once folate deficiency is confirmed in the setting of hemoglobin (Hgb) less than 12 g/dl but above 10.0 g/dl, patients will be randomized to folate supplementation or placebo. At that point, assessment of CBC/reticulocyte count and folate levels will continue every 2 weeks.
7. If Hgb is above 12.0 g/dl and no folate deficiency is identified, patients will not be randomized. Assessment of CBC/serum folate will continue every 2 weeks for the first 3 months and then monthly for a total of 6 months from the time of enrollment onto the study.
8. If folate deficiency is identified in setting of Hgb less than 10.0 g/dl, patients will not be randomized but will receive folic acid supplementation at 1 mg daily. These patients will have weekly assessments of CBC/reticulocyte count and folate levels until Hgb improves to a level above 10.0 g/dl. At that point, assessment of CBC/reticulocyte count and folate levels will change back to every 2 weeks. However, folic acid replacement will continue as initiated.

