8. STATISTICAL CONSIDERATIONS

8.1 Statistical hypotheses

- Olaparib-treated patients develop folate deficiency
- Replacing folic acid in these patients can mitigate olaparib-induced adverse events related to its hematologic toxicity (anemia, transfusion needs/number of transfusions, dose reductions and drug discontinuation)
- Folate replacement does not affect an antineoplastic effect of olaparib

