8.3 Populations for analyses

Clinical Study Protocol - 6
Olaparib - ESR-18-13807

All enrolled patients who receive at least one dose of olaparib will be included in the analysis population to be used to assess the efficacy and safety endpoints.

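### Item 11 of Section 4.1 lets patients start olaparib with Hgb below 10 g/dL, and the secondary anaemia, transfusion and olaparib-dosing comparisons neither define nor adjust their outcomes by starting Hgb

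*Combined protocol and SAP*

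**What the plan says.** **Entry.** Section 4.1 opens with a strict rule: "Patients are eligible to be included in the study only if all of the following inclusion criteria" and no exclusion criterion apply. Item 6 includes "Haemoglobin ≥ 10 g/dL with no blood transfusion in the past 28 days", and item 7 limits ECOG performance status to 0-1. Item 11 relaxes both: "Patients can be enrolled with the lab results outside of the Inclusion criteria range or a performance status = 2, if olaparib is recommended" by the treating physician "and the olaparib Package Insert is followed for dose adjustments". The unnumbered disease criterion just before item 6 already states: "Olaparib must be recommended to these patients by their treating physician".

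**Action at Hgb 10.** Section 1.1 item 8: "If folate deficiency is identified in setting of Hgb less than 10.0 g/dl, patients will not be randomized but will receive folic acid supplementation". Table 8 (Section 7.4.4.2) opens its anaemia options, including transfusion and interruption, at an absolute Hgb below 10.

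**Analysis.** Section 8.1 hypothesises: "Replacing folic acid in these patients can mitigate olaparib-induced adverse events related to its hematologic toxicity". Section 8.3: "All enrolled patients who receive at least one dose of olaparib will be included in the analysis population" for efficacy and safety. Sections 2 and 7.1.1 compare anaemia, transfusion and olaparib dosing outcomes in supplemented patients with those who did not get or need folic acid. Section 8.4.1 names Hgb before olaparib as a covariate, in the model of folate deficiency.

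**The concern.** Item 11 makes two lab-related statements in Section 4.1 incompatible: all criteria must hold, yet the lab limits may be set aside. Of its two conditions, the recommendation is met by every candidate and the Package Insert condition concerns dosing. Neither screens on Hgb.

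The line that can be set aside is the one the study later acts on. A patient who starts at, say, 9.5 g/dL is already in Table 8 territory before olaparib could have had any effect. If the secondary outcomes are tabulated on absolute Hgb, on any transfusion or on any interruption, part of what is tabulated reflects the starting value. What is at stake is the reading of the folic acid comparison, which is the study's second purpose.

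**Working it through.** **1. The plan's own figure.** Inputs from Section 8.2: null 0.50, alternative 0.66, one-sided alpha 0.05, power 80%.

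n = [(1.645 × √(0.50 × 0.50) + 0.842 × √(0.66 × 0.34)) / 0.16]² = [(0.8225 + 0.3987) / 0.16]² ≈ 58.2, so 59.

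The exact binomial test at n = 60 rejects at 37 or more deficient patients, with alpha 0.0462 and power 0.802. Attrition: 60 / 0.80 = 75. Both figures reproduce. The endpoint is serum folate below 7 ng/mL, so item 11 does not touch them.

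**2. Who can enter below 10.** Item 11 lifts inclusion ranges only. Exclusion 3 still bars persistent toxicity above grade 2 from earlier cancer therapy. Table 8 places Hgb below 8 at grade 3, so therapy-related Hgb of 8 to <10 passes. Exclusion 4 still bars MDS/AML or suggestive features. Low entry values are plausible, since prior lines are unlimited (item 10) and earlier PARP inhibitor use is allowed.

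**3. Where starting Hgb is and is not accounted for.**

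| Element | Refers to baseline Hgb? |
|---|---|
| Primary endpoint (Section 2) | Not relevant; folate only |
| Laboratory AEs (Section 7.3.7) | Yes; deterioration from baseline |
| Folate-deficiency model (8.4.1) | Yes; covariate |
| Anaemia, transfusion, interruption, dose reduction (Sections 2, 7.1.1) | No |
| Table 8 actions | No; absolute Hgb |
| Analysis population (8.3) | No; all dosed patients |

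**4. Which group they fall into.**
- Section 1.1 item 8: a low-Hgb entrant who later becomes deficient is not randomised and takes folic acid. In the Section 2 and 7.1.1 comparison, that patient sits on the supplemented side.
- Section 8.4.1: deficient patients with cytopenia of grade 2 or below are randomised 1:1. Table 8 makes Hgb 8 to <10 grade 2, so the same patient would be randomised while already anaemic.

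The two sections disagree, and starting Hgb reaches the outcomes either way.

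**5. Scale, by assumption only.** The documents give no share of entrants below 10. Assume 5% to 15% of 75, with 66% becoming deficient whatever their starting Hgb, and no attrition:
- entrants: 75 × 0.05 = 3.75 to 75 × 0.15 = 11.25;
- deficient: 3.75 × 0.66 = 2.5 to 11.25 × 0.66 = 7.4.

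For the broad comparison, assume further that n = 15 to 25 other supplemented patients have a 20% transfusion rate and that these k entrants have a rate r of 50% to 70%. The group rate is (0.20n + rk) / (n + k):
- n = 25, k = 2.475, r = 0.50: (5 + 1.2375) / 27.475 = 22.7%;
- n = 15, k = 7.425, r = 0.70: (3 + 5.1975) / 22.425 = 36.6%.

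Folic acid has no effect in either case. The second is the worst corner of assumed inputs, not an estimate.

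**The case against.** The strongest reply is that Section 8.4.1 opens the haematologic comparison with randomised patients. Under Section 1.1 item 8, low-Hgb deficient entrants are not randomised, so they fall outside it. Under Section 8.4.1's own grade rule they are randomised 1:1, which gives no systematic direction. A reader might infer that the randomised comparison is biased against folic acid; the documents do not support that. What remains is that the same sentence in 8.4.1 keeps the comparator of patients who did not get or need folic acid. That does not describe a randomised arm, and Sections 2 and 7.1.1 carry no restriction to randomised patients.

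A reader might also infer that pre-existing anaemia is counted as olaparib toxicity. No passage says so. Section 7.3.7 measures laboratory AEs against baseline, Section 7.3.5 asks for causality, and Table 8 asks for the cause to be investigated. This protects AE reporting, but not the separately listed secondary outcomes.

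Nor do the limits exclude nobody. Performance status is relaxed only to 2, and exclusions 3 and 4 stand. Item 8 also needs folate deficiency, and exclusion 1 bars folate below 7 ng/mL at entry, so a compliant patient does not meet it on day 1.

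Finally, broad entry looks deliberate in a pilot open to anyone who can benefit from olaparib. Section 4 and exclusion 11 allow exceptions independently, so changing item 11 alone would not close the route. Patients starting at 10 to <12 raise the same attribution question, because Hgb below 12 is the randomisation trigger. These last points are right, and they argue for an analysis remedy based on measured Hgb.

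**Conclusion.** The point holds for the secondary outcomes. Section 4.1 contradicts itself on lab limits, entry below Hgb 10 is possible, and the anaemia, transfusion, interruption and dose-reduction outcomes have neither a baseline-referenced definition nor planned adjustment for starting Hgb. In the broad comparison of Sections 2 and 7.1.1, low-Hgb entrants who become deficient join the supplemented side under Section 1.1 item 8. This works against folic acid if, as seems likely, a low starting Hgb brings more transfusions and interruptions. In the Section 8.4.1 comparison the issue is unadjusted anaemia at randomisation, with no fixed direction.

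The size cannot be derived from the documents. The 2 to 7 patients and the shift from 20% to 22.7%-36.6% rest wholly on assumed inputs. The primary endpoint and its sample size stand.

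**What to change.** 1. Reconcile items 6, 7 and 11 of Section 4.1 with its opening rule. Reconcile Section 1.1 item 8 with Section 8.4.1 on whether deficient patients with Hgb 8 to <10 are randomised. Which rules apply is for the sponsor to decide.
2. In Sections 8.3 and 8.4.1, keep all dosed patients in the primary folate analysis.
3. Adjust the anaemia, transfusion and olaparib-dosing comparisons for pre-olaparib Hgb. This also covers entrants at 10 to <12 and those admitted through other waivers.
4. Report the same outcomes in patients who met the plan's own item 6 Hgb limit, and list those who entered below it separately.

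The cost is plan wording and a little more analysis. The screening CBC in Section 1.1 already supplies the covariate. The restricted tables lose a few patients. With few transfusion events, the adjusted models should stay small.
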